DOSE REGIMEN	
General guidance:
 
 • All treatment regimens will be administered with meals • A daily dose of 6 mg will be given once a day in the morning and daily doses of 12 mg and higher will be administered twice daily, approximately 10 hours apart during the day. • The maximum total daily dose of SD-809 ER is 72 mg (36 mg BID), unless the subject is receiving a strong CYP2D6 inhibitor (See Appendix 11), in which case the maximum total daily dose is 42 mg 
 ○ Individual doses up to and including 12 mg are given as a single tablet ○ Individual doses of 15 to 24 mg will be given as two tablets ○ Individual doses of 27 to 36 mg will be given as three tablets • Dose increases or decreases may occur no more frequently than once per week • Dose adjustments are limited to 6 mg/day (each week) (6 mg/day or 12 mg/day after a total daily dose of 48 mg is reached). Dose reductions in increments greater than 6 mg should be reviewed with the Clinical Monitor. (See Section 5.2.5) • If a strong CYP2D6 inhibitor is started (i.e., paroxetine, fluoxetine, bupropion), the Clinical Monitor should be notified as a dose reduction of more than 6 mg may be required.

DOSE REGIMEN (continued)	Switch Subjects:			
	
 • Initial dosing regimen: Based on the subject’s tetrabenazine total daily dose, an initial dosing regimen of SD-809 ER will be assigned which targets a steady state AUC of total ($\alpha+\beta$)-HTBZ that is comparable to that of the subject’s tetrabenazine regimen: 			
	If a Switch Subject’s Incoming Total Daily TBZ Dose is:	Then, the Initial Total Daily SD-809 ER Dose Should Be:	Taken As:	
			Morning Dose	Evening Dose
	12.5 mg	→	6 mg	6 mg
	25 mg	→	12 mg	6 mg
	37.5 mg	→	18 mg	9 mg
	50 mg	→	24 mg	12 mg
	62.5 mg	→	30 mg	15 mg
	75 mg	→	36 mg	18 mg
87.5 mg	→	42 mg	21 mg	
100 mg	→	48 mg	24 mg	

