1.4 SD-809 (*d*₆-Tetrabenazine)

SD-809 is a deuterated analog of tetrabenazine in which the two O-linked methyl groups (CH₃) of the tetrabenazine molecule have been replaced by two trideuteromethyl groups (CD₃). The conversion of SD-809 and tetrabenazine to their active metabolites, α-HTBZ and β-HTBZ, proceeds similarly in human liver S9 fraction and in human liver microsomes. The CD₃ groups in SD-809, which are conserved in α-HTBZ and β-HTBZ, attenuate the metabolism of these active metabolites by CYP2D6 relative to the non-deuterated metabolites from tetrabenazine, leading to longer *in vitro* half-lives in human liver microsomes, human liver S9 fraction and in cells transfected with CYP2D6. These pharmacokinetic benefits have been confirmed in a clinical setting and enable less frequent dosing and reduced the plasma fluctuation of the active metabolites. Furthermore, the attenuated metabolism achieved through deuteration reduces the impact of CYP2D6 genotype on exposure as compared to tetrabenazine, with the potential to simplify dosing.

The safety and pharmacokinetics of oral SD-809 have been evaluated in five Phase 1 studies in healthy adult volunteers. Single doses of SD-809 (either as an immediate-release or as an extended-release [ER] formulation) have been administered to 130 subjects at doses ranging from 7.5 to 24 mg, either alone or in conjunction with CYP2D6 inhibition. Multiple dose regimens of the ER formulation have also been administered to 24 of those subjects for up to 5 days (at doses up to 22.5 mg twice daily [BID] for 3 days).

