For all studies, plasma concentrations of parent drug were low and sporadic because of the rapid and extensive hepatic metabolism of SD-809 to the active metabolites *d*₆-α-HTBZ and *d*₆-β-HTBZ. Peak plasma concentrations of the active moieties *d*₆-α-HTBZ and *d*₆-β-HTBZ were reached within 1 to 1½ hours post-dosing following administration of an immediate release formulation. Peak plasma concentrations were significantly later (median *t*_{max} 3 to 4 hours) and lower for the ER formulation without a comparable loss of exposure. In all studies where tetrabenazine was included as a control arm, deuteration was shown to significantly prolong the half-lives of both α - and β-HTBZ, resulting in an increase in exposure (~130% increase) for both active metabolites at comparable doses. Based on the pharmacokinetics over a dose range of 7.5-22.5 mg SD-809 ER, it is estimated that a 6 mg dose of SD-809 will provide an exposure (AUC_(inf)) comparable to 12.5 mg of tetrabenazine. Inhibition of CYP2D6 metabolism by paroxetine administration led to a 3-fold increase in bioavailability of *d*₆-(α+β)-HTBZ, comparatively less than has been reported with in a similar drug interaction study with tetrabenazine.

To date, five Phase 1 studies in healthy volunteers have been conducted with SD-809, including two with an immediate release formulation (powder in capsule) (AUS-SD-809-CTP-06, SD-809-C-12) and three with extended release formulations (AUS-SD-809-CTP-07 Part 1 and Part 2 and

SD-809-C-08, SD-809-C-11). In total, 100 subjects have received single doses of SD-809 or SD-809 ER, ranging from 7.5 to 22.5 mg and 24 subjects have received repeated doses of SD-809 ER for up to 5 days at 22.5 mg BID. In these studies, no SAEs were reported and all AEs were mild to moderate in intensity. Commonly reported AEs included headache, somnolence, nausea, dizziness and vessel puncture reaction. When tetrabenazine was used as a comparator, the adverse events of SD-809 were qualitatively similar to tetrabenazine. The adverse events reported with SD-809 were also consistent with prior clinical experience with tetrabenazine.

Additional information on the study results may be found in the SD-809 ER Investigator's Brochure.

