3.3 Rationale for Dose Selection

As with tetrabenazine, SD-809 ER treatment will be individualized, and, therefore fixed doses will not be evaluated in the study. The starting dose of 6 mg of SD-809 ER provides an AUC of total ($\alpha+\beta$)-HTBZ that is comparable to the 12.5 mg starting dose of tetrabenazine, but with a lower peak concentration and higher trough concentration. The dose level of SD-809 ER treatment will be evaluated on a weekly basis during the titration/dose adjustment period, based on assessments of chorea control and adverse events, in order to determine if dose adjustment is needed. This approach is consistent with the tetrabenazine prescribing information.

Dose adjustments should occur in increments of 6 mg/day (each week) (6 mg/day or 12 mg/day after a total daily dose of 48 mg is reached). Dose reductions in increments greater than 6 mg should be reviewed with the Clinical Monitor (See Section 5.2.5).

The maximum total daily dose of SD-809 ER is 72 mg per day, unless the subject is receiving a strong CYP2D6 inhibitor (e.g., paroxetine, See Appendix 11), in which case the maximum total daily dose is 42 mg.

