5 STUDY TREATMENT

The study medication to be used in this trial is an extended release (ER) formulation of SD-809. Three dose strengths of SD-809 ER will be available for use: 6, 9, and 12 mg tablets. Each dose strength will have a black marking of SD 6, SD 9 or SD 12, corresponding to the dose strength and a distinct tablet color: 6 mg - purple; 9 mg - blue; 12 mg - beige.

5.1 *Investigational Product*

The investigational product is a matrix formulation and is designed as a gastro-erosional, extended release tablet to be administered with food. Study drug is coated with a colored polymer coating to aid in swallowing. The colored polymer coating is applied to the tablets according to dose strength; 6 mg - purple; 9 mg - blue; 12 mg - beige. Each dose strength will have a black marking of SD 6, SD 9 or SD 12, corresponding to the dose strength. SD-809 ER tablets have been manufactured according to current Good Manufacturing Practices regulations. During titration/dose adjustment, SD-809 ER tablets will be supplied in weekly blister packs as 6, 9, and/or 12 mg tablets and will be labeled according to applicable regulatory guidelines. Each blister pack will contain a sufficient supply of drug until the next specified visit, plus overage to account for potential delays in study visits or evaluations or receipt of their supplies. **Once the investigator determines that a stable dose has been reached, SD-809 ER will be supplied in 30 count containers and labeled according to applicable regulatory guidelines.**

Complete details regarding SD-809 ER supply, dispensing and ordering will be provided in the study Operations Manual.

SD-809 ER tablets must be stored in a secure area with access limited to authorized staff, protected from light at controlled room temperature, 15°C to 25°C (59°F to 77°F).

5.2 *Treatment Regimen*

5.2.1 *General Guidelines*

The following general guidance applies to treatment regimens for all subjects in the study:

- All treatment regimens will be administered with meals
- A daily dose of 6 mg will be given once a day in the morning and daily doses of 12 mg and higher will be administered twice daily, approximately 10 hours apart during the day.
- The maximum total daily dose of SD-809 ER is 72 mg (36 mg BID), unless the subject is receiving a strong CYP2D6 inhibitor (See Appendix 11), in which case the maximum total daily dose is 42 mg
 - Individual doses up to and including 12 mg are given as a single tablet

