5.2.2 Dosing in Switch Subjects

For Switch subjects, the initial SD-809 ER dosing regimen will be based on the subject's incoming total daily dose of tetrabenazine. As outlined in Table 1 and Appendix 14, an initial dosing regimen of SD-809 ER will be assigned which targets a steady state AUC of total ($\alpha+\beta$)-HTBZ that is comparable to that of the subject's tetrabenazine regimen (Table 1).

After initial dose conversion, the investigator may adjust the dose of SD-809 ER upward or downward over the following 4 weeks, if necessary, to a level in which adequate chorea control has been achieved and the subject is tolerating the treatment regimen. Changes in dose should not be made more often than once per week unless the subject is experiencing an intolerable adverse event.

Once adequate control of chorea has been achieved, the dose of study drug should not be increased further.

Pharmacokinetic modeling and simulation of Phase 1 data were performed to estimate the overall systemic exposure (AUC) for various tetrabenazine and SD-809 ER regimens. Appendix 14 depicts the values for AUC₀₋₂₄ for extensive and intermediate metabolizers of CYP2D6.

Based on the data in Appendix 14, an initial SD-809 ER regimen has been identified which approximates the AUC₀₋₂₄ for total ($\alpha+\beta$)-HTBZ of the corresponding tetrabenazine total daily dose in CYP2D6 extensive and intermediate metabolizers (Table 1). Although the median AUCs for SD-809 ER are slightly lower than those for the corresponding tetrabenazine regimen, there is considerable overlap in the distributions of this parameter. Subjects with diminished CYP2D6 function (e.g., poor metabolizers or receiving potent CYP2D6 inhibitors) who undergo dose conversion according to Table 1 may have an initial AUC on SD-809 ER that is up to 30-40% below that of their tetrabenazine regimen (See Appendix 15). As with intermediate and extensive metabolizers, there is considerable overlap in the distribution of AUCs between SD-809 and tetrabenazine in poor metabolizers. Furthermore, subjects with inadequate control of chorea may undergo dose adjustment for the four weeks following initial dose conversion. Additional dose adjustments may be made after Week 4 if clinically indicated.

Table 1: Initial SD-809 Dose Regimen based on Incoming Tetrabenazine Regimen

If a Switch Subject's Incoming Total Daily TBZ Dose is:	Then, the Initial Total Daily SD-809 ER Dose Should Be:	Taken As:	
		Morning Dose	Evening Dose

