Appendix 10: Swallowing Disturbance Questionnaire (SDQ)

Appendix 11: Strong CYP2D6 Inhibitors

Subject's receiving any of these strong CYP2D6 inhibitors will have a maximal dose of SD-809 ER of 42 mg per day.

- Bupropion
- Fluoxetine
- Paroxetine

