Subjects receiving a strong CYP2D6 inhibitor or who are poor CYP2D6 metabolizers are considered to have impaired CYP2D6 function. The following AE analyses will be repeated by impaired CYP2D6 function category at baseline (subjects receiving a strong CYP2D6 inhibitor at Baseline, subjects not receiving a strong CYP2D6 inhibitor at Baseline, CYP2D6 poor metabolizers, non-CYP2D6 poor metabolizers, subjects with impaired CYP2D6 function, and subjects without impaired CYP2D6 function):

- Overview of TEAEs
- TEAEs by SOC and preferred term

For TEAE summaries, if a subject has more than one TEAE within a preferred term, the subject is counted once in that preferred term at the maximum severity and at the closest relationship to study drug. If a subject has more than one TEAE within a system organ class, the subject is similarly counted once in that system organ class.

Complete listings of all AEs will be provided. In addition, data listings of all SAEs, AEs leading to withdrawal from the study, and AEs leading to death will also be provided.

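### The 42 mg/day SD-809 ER maximum covers users of strong CYP2D6 inhibitors but not subjects already known to be CYP2D6 poor metabolizers, and the documents give no reason for the difference

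*Protocol*

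**What the plan says.** The lower SD-809 ER maximum appears four times in the protocol, each time for inhibitor users only:

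- Synopsis, Dose Regimen: the 72 mg maximum holds "unless the subject is receiving a strong CYP2D6 inhibitor (See Appendix 11), in which case the maximum total daily dose is 42 mg".
- Section 3.3: "The maximum total daily dose of SD-809 ER is 72 mg per day, unless the subject is receiving a strong CYP2D6 inhibitor".
- Section 5.2.1: "The maximum total daily dose of SD-809 ER is 72 mg (36 mg BID), unless the subject is receiving a strong CYP2D6 inhibitor".
- Appendix 11: subjects on any of the listed "strong CYP2D6 inhibitors will have a maximal dose of SD-809 ER of 42 mg per day". The list is bupropion, fluoxetine and paroxetine.

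No exclusion criterion removes poor metabolizers, and no dosing rule limits them below 72 mg.

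Elsewhere the two groups are put together. SAP 9.9.1 states: "Subjects receiving a strong CYP2D6 inhibitor or who are poor CYP2D6 metabolizers are considered to have impaired CYP2D6 function". It tabulates them jointly and also separately. Protocol 5.2.2 speaks of "Subjects with diminished CYP2D6 function (e.g., poor metabolizers or receiving potent CYP2D6 inhibitors", and refers both to Appendix 15 for the exposure expected after the initial conversion.

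The protocol also acts on metabolizer status that is already known. The footnote to the eligibility criteria limits incoming tetrabenazine to 50 mg/day, instead of 100, when CYP2D6 function is known to be impaired. Citalopram is barred in known CYP2C19 poor metabolizers (Appendix 16). The study's own CYP2D6 genotype is blinded (3.2).

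**The concern.** Take two subjects whom the SAP places in one impaired-function class. One uses paroxetine and must stop at 42 mg/day. The other is known from earlier testing to be a poor metabolizer and may continue to 72 mg/day. Section 3.3, whose purpose is to explain dose selection, states both maxima without saying why they differ.

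What is at stake is the protection of individual subjects, not the analysis. No summary table is expected to change. Blinding explains why the study genotype cannot set a cap. It does not explain disregarding a status that the site already knows, since the tetrabenazine limit relies on that same knowledge.

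**Working it through.** **Inputs.** Appendix 15 gives simulated steady-state AUC24 (h·ng/mL) in poor metabolizers. SD-809: 1061 at 12 mg, 1740 at 18 mg, 2435 at 24 mg. Tetrabenazine: 1510 at 25 mg, 2750 or 2768 at 37.5 mg, 4200 [2296-8155] or 4228 [2394-8030] at 50 mg, depending on regimen. The protocol gives no derivation of 42 mg or 72 mg to reproduce.

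**Step 1: the plan's own figure.** Section 5.2.2 says that AUC after conversion may be up to 30-40% lower in both impaired groups, citing Appendix 15.

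- 25 to 12 mg: 1 − 1061/1510 = 30%
- 37.5 to 18 mg: 1 − 1740/2750 = 37% (also 37% with 2768)
- 50 to 24 mg: 1 − 2435/4200 = 42% (also 42% with 4228)

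This agrees closely, slightly above 40% at the top dose. It confirms that the protocol uses the poor-metabolizer simulation for inhibitor users as well.

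**Step 2: ratio of the caps.** 72/42 = 1.71.

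**Step 3: exposure at each cap.** AUC per mg rises with dose: 1061/12 = 88.4, 1740/18 = 96.7, 2435/24 = 101.5. Proportional scaling alone would therefore be too narrow, so a linear and a power fit to the three medians are added. All values extrapolate beyond the simulated 12-24 mg.

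| Scaling | AUC at 42 mg | AUC at 72 mg |
|---|---|---|
| Proportional from 12 mg | 3714 | 6366 |
| Proportional from 18 mg | 4060 | 6960 |
| Proportional from 24 mg | 4261 | 7305 |
| Linear: 114.5 × dose − 315.7 | 4493 | 7928 |
| Power: 53.9 × dose^1.20 | 4782 | 9130 |

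Against tetrabenazine 50 mg/day, with the lowest value over 4228 and the highest over 4200:

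- 42 mg: 3714/4228 = 0.88 to 4782/4200 = 1.14
- 72 mg: 6366/4228 = 1.51 to 9130/4200 = 2.17

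The 72 mg medians lie inside the widest tetrabenazine 50 mg interval (2296-8155), except under the power fit.

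**Step 4: path to the cap.** A Switch subject with known impairment on tetrabenazine 50 mg starts at 24 mg (Table 1). With steps of 6 mg, and 12 mg once 48 mg is reached, the quickest path is 24-30-36-42-48-60-72: 42 mg at the third increase and 72 mg at the sixth. A Rollover subject starting at 6 mg reaches 42 mg at the sixth and 72 mg at the ninth. Throughout, chorea must stay uncontrolled with no limiting adverse event.

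**Step 5: how many subjects.** The documents give no frequency. Assume that 2-10% are poor metabolizers and that 10-50% of those know their status. Among 36 Switch subjects the expected number is 36 × 0.02 × 0.10 = 0.07 to 36 × 0.10 × 0.50 = 1.8. The chance of enrolling at least one is 1 − 0.998^36 = 7% to 1 − 0.95^36 = 84%. Rollover subjects cannot be estimated.

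**The case against.** The strongest defence is that the split is deliberate. Section 1.2 lists the need for genotyping as a drawback of tetrabenazine. Section 1.4 says that deuteration "reduces the impact of CYP2D6 genotype on exposure as compared to tetrabenazine, with the potential to simplify dosing". Section 3.2 blinds genotype so that the effect of phenotype on safety can be evaluated. Inhibitor use, unlike genotype, is visible from concomitant medication. The Investigator's Brochure, which is not among the documents, may hold a pharmacokinetic reason. It stands that a reason may exist outside the documents, but the reasons inside them do not separate the groups:

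- **Attenuation.** Section 1.4 describes inhibition in similar terms: a 3-fold rise under paroxetine, "comparatively less than has been reported with in a similar drug interaction study with tetrabenazine". Inhibitor users are capped all the same.
- **Titration to response and safety review.** The stopping rules and the Clinical Monitor's monthly review apply equally to inhibitor users.
- **An inhibitor started mid-study.** That has its own rule, notifying the Clinical Monitor. The cap also binds a subject on a stable antidepressant for at least 8 weeks before Screening, whose inhibition is present from the first SD-809 dose, as genotype is.

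A second objection is that equivalence of the two groups is assumed. It stands that the readable text compares no effect sizes: Appendix 15 covers poor metabolizers only, and no ratio to extensive metabolizers is given for SD-809. A reader should therefore not infer that the two effects are equal in size. But 5.2.2 and SAP 9.9.1 make the grouping themselves.

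A third objection, that a 42 mg cap leaves a poor metabolizer little room above tetrabenazine 50 mg, is correct. It counts as a cost of the fix.

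**Conclusion.** The inconsistency holds on the text: two groups that the plan treats alike elsewhere have SD-809 ER maxima differing by a factor of 1.71, and the documents do not say why. A known poor metabolizer could reach a median AUC about 1.5 to 2.2 times that of tetrabenazine 50 mg/day at 72 mg, against about 0.9 to 1.1 times at 42 mg. These ranges rest on extrapolating three simulated medians up to three-fold in dose, and they depend on the scaling model. The textual finding does not.

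Two stronger readings are tempting and are not supported:

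- That 72 mg is unsafe in poor metabolizers. Tetrabenazine 50 mg is a reference point, not a limit set for SD-809. Even in unimpaired subjects, 72 mg is 72/48 = 1.5 times the Table 1 conversion of the 100 mg tetrabenazine maximum.
- That the 7-84% is the chance of the problem occurring. It is the chance of enrolling a known poor metabolizer under assumed inputs. The further chance that this subject goes above 42 mg is unknown, and few subjects, possibly none, would.

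This is a cheap safety improvement, not a demonstrated harm.

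**What to change.** In the synopsis, 3.3, 5.2.1 and Appendix 11, extend the 42 mg/day maximum to any subject known at entry to be a CYP2D6 poor metabolizer. Apply it to further dose increases. Refer to the Clinical Monitor any such subject who is already stable above 42 mg, rather than stepping the dose down automatically, and any whose chorea is inadequately controlled at 42 mg. Keep the study genotype blinded. If the sponsor has a pharmacokinetic reason for the split, a sentence in 3.3 stating it would also remove the inconsistency.

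The change is one clause in four places, with no new test and no unblinding. Initial conversion is unaffected, since the 50 mg tetrabenazine limit converts to at most 24 mg. The costs are:

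- Known poor metabolizers lose dose headroom, as inhibitor users already do.
- Poor metabolizers of unknown status stay uncapped, so the end-of-study phenotype evaluation mixes two dosing rules for a few subjects.
- The Clinical Monitor has slightly more to review.

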Appendix 16: Celexa and Lexapro (Cipralext) Dosing Information	125

LIST OF ABBREVIATIONS

Abbreviation	Definition
\leq	Less than or equal to
\geq	Greater than or equal to
°C	Degrees Celsius
°F	Degrees Fahrenheit
ADL	Activities of Daily Living
AE	Adverse Event
ALP	Alkaline phosphatase
ALT	Alanine aminotransferase
AST	Aspartate transaminase
AUC	Area Under Curve
BARS	Barnes Akathisia Rating Scale
BID	Twice daily
BUN	Blood urea nitrogen
C	Carbon
CAG	Cytosine Adenine Guanine
CFR	Code of Federal Regulations
cGMP	Current Good Manufacturing Practice
C _{max}	Maximum concentration
CNS	Central nervous system
eCRF	Electronic Case Report Form
CRO	Contract Research Organization
C-SSRS	Columbia Suicide Severity Rating Scale
CTCC	Clinical Trials Coordination Center
CYP2D6	Cytochrome P ₄₅₀ 2D6
CYP ₄₅₀	Cytochrome P ₄₅₀
D, d	Deuterium
DSM-IV	Diagnostic and Statistical Manual of Mental Disorders, 4 th Edition
ECG	Electrocardiogram
ER	Extended Release
ESS	Epworth Sleepiness Scale
EU	European Union

Abbreviation	Definition
FDA	Food and Drug Administration
FSH	Follicle Stimulating Hormone
g	Grams
GCP	Good Clinical Practice
H	Hydrogen
HADS	Hospital Anxiety and Depression Scale
HBsAg	Hepatitis B surface antigen
hCG	Human chorionic gonadotropin
HD	Huntington disease
HIV	Human immunodeficiency virus
HTBZ	Dihydrotetrabenazine
IB	Investigator's Brochure
ICF	Informed Consent Form
ICH	International Conference on Harmonization
IEC	Independent Ethics Committee
IRB	Institutional Review Board
IUD	Intrauterine device
Kg	Kilogram
LDH	Lactate dehydrogenase
MAO	Monoamine oxidase
MCV	Mean cell volume
mg	Milligram
min	Minute
mL	Milliliter
MoCA [®]	Montreal Cognitive Assessment
ms	Millisecond
NINDS	National Institute of Neurological Disorders & Stroke
O	Oxygen
PK	Pharmacokinetic
PR	PR interval - measured from the beginning of the P wave to the beginning of the QRS complex
QRS	QRS duration (complex) - a structure on the ECG that corresponds to the depolarization of the ventricles

Abbreviation	Definition
QT	QT interval - a measure of the time between the start of the Q wave and the end of the T wave in the heart's electrical cycle
QTcF	Fridericia-corrected QT interval
RBC	Red blood cell
SAE	Serious Adverse Event
SDQ	Swallowing Disturbance Questionnaire
SF-36	Short Form 36 Health Survey
SOP	Standard Operating Procedure
SSRI	Selective serotonin reuptake inhibitor
TBZ	tetrabenazine
TMC	Total maximal chorea score
TFC	Total functional capacity
t_{\max}	Time of maximum drug concentration
UHDRS	Unified Huntington's Disease Rating Scale
UPDRS	Unified Parkinson's Disease Rating Scale
US	United States
VMAT	Vesicular monoamine transporter

